9.2 Screening Procedures

Members of the patient's existing direct care team will have access to patient records for discussion at the Guy's and St Thomas' hospital NHS Trust (GSTT) severe asthma clinic meetings.

Where the participant has been approved to receive benralizumab for clinical reasons and they meet the inclusion criteria for the study, the identified participant will then be approached by a member of the GSTT asthma direct care team who will discuss the study in detail with their patient. The patient will be given a copy of the participant information sheet (PIS) or one will be sent to them by post or email to consider before their next scheduled clinic visit. The patient will be given adequate time to decide whether or not they wish to take part in the study and be encouraged to ask any questions.

9.3 Schedule of assessments for each visit

See also section 7.2

Design and patient flow:

Visit 1: Consent, Enrollment and schedule of visit dates

Visit 2: Day 1 Covid-19 test

Visit 3: Day 2 Bronchoscopy

Visit 4: Day 10 Subject receives benralizumab dose 1 (30mg subcutaneous injection)

Visit 5: Day 38 Subject receives benralizumab dose 2 (30mg subcutaneous injection)

Visit 6: Day 66 Subject receives benralizumab dose 3 (30mg subcutaneous injection)

Visit 7: Day 83 Covid-19 test

Visit 8: Day 84 Bronchoscopy

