The BEUTI study will examine how benralizumab affects the structure and function of the airway cells in people with severe eosinophilic asthma and how the immune function of these cells changes with treatment. The aim is to take samples of cells from the airways during a bronchoscopy (a camera test looking into the lungs) before starting benralizumab and after 12 weeks of treatment. These investigations will allow us to better understand how benralizumab affects the cells within the airways.

All potential participants with severe eosinophilic asthma (according to standard NICE criteria for biologic eligibility under the NHS) who have already been approved for this treatment in the severe asthma multidisciplinary meeting at Guy's & St Thomas' NHS Trust will be approached for this study. Agreement to take part in this study, will not significantly delay treatment initiation for these patients by more than a few weeks. Potential participants will be provided with further written information about the study in the form of the patient information sheet (PIS). They will be given ample time to read this and there will be a contact telephone number in the PIS should they wish to contact the research team for further information.

Hypothesis:

The depletion of eosinophils by benralizumab leads to additional inhibitory effects on T2 inflammation which collectively underpins the improvements in multiple clinical domains and reduction in T2 biomarkers observed in real world cohort studies.

The important research questions we will aim to answer:

- i) What is the effect of benralizumab on T2 signalling. Can benralizumab modulate T2-signalling and/or gene expression in addition to triggering eosinophil and basophil depletion?
- ii) What additional cell types (e.g. ILC2, alveolar macrophages, mast cells, bronchial epithelial cells, airway smooth muscle) are regulated by benralizumab?
- iii) Does the marked reduction in exacerbations observed with benralizumab partly reflect restoration of the deficient anti-viral immune responses seen in patients with severe asthma?

6 Trial objectives and purpose

Primary Objective:

To determine if benralizumab leads to a reduction in T2 mediators and/or activation in airway cells in patients with severe eosinophilic asthma.

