7.1 Study Design

This is a prospective open label phase IV observational study

Primary Endpoint:

Change in the number / proportion of T2 related cellular populations in BAL including ILC2, Th2, alveolar macrophages, eosinophils and basophils pre- and post benralizumab (12 weeks).

Secondary Endpoints:

1. Change in cellular populations and gene expression of T2-related signalling pathways in bronchial biopsies pre- and post benralizumab
2. Change in type 1 & 3 interferon production and viral replication following infection of cultured BECs and alveolar macrophages with RV-16 and examine the response of cells to SARS-CoV-2 collected pre- and post- benralizumab.
3. Change in cellular populations and gene expression of remodelling-related pathways in bronchial biopsies pre- and post benralizumab
4. Change in airway oscillometry measures and MRI measures of ventilation pre- and post benralizumab.

Each recruited participant will be in the study for 3 months and will attend for 8 visits including screening and informed consent. Visits will include blood, breathing tests and bronchoscopy. Participants will undergo bronchoscopy twice in a 12 week period (pre- and 12 weeks post benralizumab treatment). Processing of biological samples and data from clinical measures will be mined throughout the study period of 24 months and also when patients revert to ongoing NHS clinical care that is standard for those on benralizumab treatment for their asthma.

Gantt Chart: The total study duration is 24 months.

Months	3	6	9	12	15	18	21	24
Ethics application and approval								
Patient recruitment, bronchoscopies and sample collection and laboratory procedures								
BEC and mac culture for anti-viral immunity								
BEC and Br biopsy Spatial transcriptomics								
Protein analysis								
Data analysis								
Manuscript(s) preparation								

Treatment Regimen:

Benralizumab will be commenced according to UK NICE severe asthma guidance with 30mg sc dosing every 4 weeks for first 3 doses, followed by every 8 weeks.

Design and patient flow:

- Visit 1: Consent, Enrollment and schedule of visit dates
- Visit 2: Day 1 Covid-19 test
- Visit 3: Day 2 Bronchoscopy
- Visit 4: Day 10 Subject receives benralizumab dose 1 (30mg subcutaneous injection)
- Visit 5: Day 38 Subject receives benralizumab dose 2 (30mg subcutaneous injection)
- Visit 6: Day 66 Subject receives benralizumab dose 3 (30mg subcutaneous injection)
- Visit 7: Day 83 Covid-19 test

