7.2 Flowchart

	Screening Visit	Study visits						
Visit Number	1	2	3	4	5	6	7	8
Day		1	2	10	38	66	93	94
Full medical history, confirmation of SEA, medication review	X							
Physical examination	X	X	X	X	X	X	X	X
Current/recent medications, side effects	X		X	X	X	X	X	X
Nasal and/or throat swab for COVID-19 testing (PCR)		X					X	
Benralizumab				X	X	X		
Bronchoscopy			X					X

	Screening Visit	Study visits							
		1	2	3	4	5	6	7	8
Visit Number									
Day		1	2	10	38	66	93	94	
COVID PCR		Bronch 1	benra dose 1	benra dose 2	benra dose 3	COVID PCR	Bronch 2		
FeNO	X		X	X	X	X			X
Spirometry	X		X	X	X	X			X
Oscillometry	X		X	X	X	X			X
ACQ-6	X		X	X	X	X	X		X
mAQLQ	X		X	X	X	X	X		X
Blood	X		X	X	X	X	X		X
Urine pregnancy test (females only)	X			X					
Collection of adverse events (AE)		X	X	X	X	X	X		X

8 Subject selection

Population:

Adult patients with poorly-controlled severe eosinophilic asthma referred to Guy's Severe Asthma Centre, Guy's & St Thomas' NHS Trust, who meet NICE criteria to commence biologic therapy with benralizumab. Following review of eligibility criteria potential participants will be provided with further written information about the study in the form of the Patient Information Sheet (PIS). They will be given ample time to read this and there will be a contact telephone number in the PIS should they wish to contact the research team for further information.

This is a single centre study.

Each recruited participant will be in the study for 3 months and will attend for 8 visits including screening and informed consent. Visits will include blood, breathing tests and bronchoscopy. Participants will undergo bronchoscopy twice in a 12 week period (pre- and 12 weeks post benralizumab treatment). Processing of biological samples and data from clinical measures will be mined throughout the study period of 24 months and also when patients revert to ongoing NHS clinical care that is standard for those on benralizumab treatment for their asthma.

Retention:

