10.3 Sample Analysis Procedures

The aim is to study the influence of benralizumab on structural and inflammatory airway cells in patients with severe eosinophilic asthma.

Our primary outcome measure is:

The change in the number / proportion and/or activation status of Type-2 related cellular populations in samples derived from bronchoscopy including bronchial biopsies, bronchoalveolar lavage (BAL) and bronchial brushings. These cells include ILC2, Th2, alveolar macrophages, epithelial cells, eosinophils and basophils pre- and post- 12 weeks of benralizumab using molecular techniques.

Secondary Endpoints:

To investigate the following before and after completing treatment with 12 weeks of benralizumab.

1. Changes in epithelial barrier integrity using cell biology methods such as transepithelial resistance or barrier permeability.
2. Changes in epithelial antiviral responses in untreated vs respiratory virus-infected cells including rhinovirus-16 and SARS-CoV-2 using protein and nucleic acid analyses.
3. Changes in the antiviral responses of alveolar macrophages to rhinovirus-16 or other respiratory virus infection using protein and nucleic acid analyses.
4. Changes in epithelial responses to cytokines/chemokines and/or exposure to other cell types (co-cultures).
5. Changes in airway remodelling by histological examination.
6. Changes in the profile and function of isolated structural cells (such as airway smooth muscle and epithelial cells but not restricted to) dissected from larger biopsies by molecular and cellular methods.
7. To evaluate the impact on peripheral airways by obtaining bronchoalveolar lavage (BAL) and performing nucleic acid and protein analyses
8. Peripheral airway dysfunction using tests such as impulse oscillometry but not restricted to.
9. Change in FeNO levels.

Study procedures- Clinical Assessment

The CRF will be completed and include clinical details about asthma and other relevant medical conditions and medications.

Spirometry

Spirometry will be conducted in hospital using a spirometer conforming to ATS/ERS standards as specified by the manufacturer's instructions. FEV1 (L), FVC (L), FEV1/FVC ratio, FEF25-75 (% of predicted value) and PEF (L/min) will be recorded. FEV1, FVC and PEF will be documented as both absolute values and as a percentage of the predicted value.

Oscillometry

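### Sections 7.1 and 9.3 put the only post-treatment bronchoscopy on Day 84, 10.6 weeks after dose 1; the 7.2 flowchart says Day 94, which alone gives the 12 weeks the primary endpoint requires

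*Protocol*

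**What the plan says.** **Visit lists.** Protocol section 7.1 ends its patient flow with "Visit 7: Day 83 Covid-19 test" and then "Visit 8: Day 84 Bronchoscopy". Section 9.3 repeats the same list and refers the reader to section 7.2.

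**Flowchart.** The day row in section 7.2, for Visits 2 to 8, reads "1 2 10 38 66 93 94". Visit 7 is therefore on Day 93 and Visit 8 on Day 94.

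**Where they agree.** All three give the first bronchoscopy on Day 2 and benralizumab on Days 10, 38 and 66.

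**The interval the endpoints need.**
- Primary endpoint, section 7.1: "alveolar macrophages, eosinophils and basophils pre- and post benralizumab (12 weeks".
- Primary outcome measure, section 10.3: "eosinophils and basophils pre- and post- 12 weeks of benralizumab using molecular techniques".
- Secondary endpoints, section 10.3: "before and after completing treatment with 12 weeks of benralizumab".
- Study aim, synopsis and section 5: "before starting benralizumab and after 12 weeks of treatment".
- Sections 7.1 and 8: "Participants will undergo bronchoscopy twice in a 12 week period (pre- and 12 weeks post benralizumab treatment".

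No section says which schedule governs, and none gives a window for Visit 8.

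**The concern.** Visit 8 is the only bronchoscopy after treatment starts. It provides the lavage for the primary endpoint and the biopsies and brushings for the other sample-based endpoints. A site working from 7.1 or 9.3 would take those samples 10 days earlier than a site team working from the flowchart, and short of the interval that defines the endpoint.

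Two things are at stake. If everyone follows the lists, a result at about 10.6 weeks is reported as a 12-week result. If staff use both schedules, time on drug varies between patients by an amount nobody planned, in a paired comparison of only 12 patients. Because the procedure is invasive, a mistimed sample cannot readily be taken again.

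**Working it through.** **Inputs**

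| Item | Day | Source |
|---|---|---|
| Bronchoscopy 1 (Visit 3) | 2 | 7.1, 7.2, 9.3 |
| Dose 1 (Visit 4) | 10 | 7.1, 7.2, 9.3 |
| Dose 2 (Visit 5) | 38 | 7.1, 7.2, 9.3 |
| Dose 3 (Visit 6) | 66 | 7.1, 7.2, 9.3 |
| Bronchoscopy 2 (Visit 8) | 84 | 7.1, 9.3 |
| Bronchoscopy 2 (Visit 8) | 94 | 7.2 |

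**Step 1: try to reproduce the stated 12 weeks.** Interval in weeks = (day of bronchoscopy 2 − anchor day) / 7.

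| Anchor | Day 84 | Day 94 |
|---|---|---|
| Dose 1 (Day 10) | 74 d = 10.57 wk | 84 d = 12.00 wk |
| Bronchoscopy 1 (Day 2) | 82 d = 11.71 wk | 92 d = 13.14 wk |
| Day 1 | 83 d = 11.86 wk | 93 d = 13.29 wk |
| Dose 3 (Day 66) | 18 d = 2.57 wk | 28 d = 4.00 wk |

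Time on drug runs from dose 1. On that anchor Day 84 does not reproduce 12 weeks and Day 94 reproduces it exactly. Day 84 comes close only when the count starts at Day 1 or Day 2, and those counts include 8 or 9 days before any benralizumab is given.

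**Step 2: solve for the day.** 10 + 12 × 7 = 94.

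**Step 3: size of the shortfall.** 84 − 74 = 10 days; 10 / 84 = 11.9% of the intended interval.

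**Step 4: compare with the dosing tolerance.** Section 12.2 excludes a patient whose second or third dose is more than 7 days off schedule. That window does not apply to the bronchoscopy, and at 7 days it is smaller than the 10-day gap. If dose 3 is given 7 days late, on Day 73, a Day 84 bronchoscopy follows it by 84 − 73 = 11 days, against 94 − 73 = 21 days for Day 94.

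**Step 5: how firmly is 12 weeks fixed?** The interval is written as 12 weeks 14 times: synopsis 4, section 5 once, section 6 four times, section 7.1 twice, section 8 once, section 10.3 twice (4 + 1 + 4 + 2 + 1 + 2 = 14). An interval of 10.6 weeks appears nowhere.

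**The case against.** **The wording about two bronchoscopies favours Day 84.** Sections 7.1 and 8 say both procedures fall within a 12-week period. Day 2 to Day 84 is 82 days (11.7 weeks) and fits; Day 2 to Day 94 is 92 days (13.1 weeks) and does not. This is real evidence for Day 84. The same sentence, however, also places the second procedure 12 weeks after benralizumab, which Day 84 misses. Neither day satisfies the whole sentence, so it needs correcting whichever day is chosen.

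**No section states outright that the 12 weeks run from dose 1.** That is correct. It is, though, the natural meaning of 12 weeks of a drug, and the wording in section 10.3 leaves little room for another.

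**Both days follow all three doses.** Section 12.2 stresses the effect of three doses, and Day 84 and Day 94 both come after the third. The comparison is paired with no control arm, so a uniform schedule creates no imbalance between groups. This limits the likely harm. It does not make a 10.6-week sample a 12-week one, nor does it deal with patients being sampled on different schedules.

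**The 10 days is nominal.** Doses may move by up to 7 days, and section 10.3 reschedules a bronchoscopy after an exacerbation in the preceding 6 weeks, so actual intervals will vary. This stands, and it is a reason to give Visit 8 a window as well as a corrected day.

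**Conclusion.** The concern holds. The protocol contradicts itself on the day of its only post-treatment bronchoscopy, and of the two days given only Day 94 matches the primary endpoint. Following 7.1 or 9.3 as written shortens time on benralizumab by 10 days (74 instead of 84, 10.6 weeks instead of 12.0) and time since dose 3 from 28 to 18 days, nominally for all 12 patients.

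This rests on one assumption: that the 12 weeks are counted from dose 1. It does not rest on any claimed bias, because the documents do not show how much cell populations or gene expression would change over those 10 days. The sample size and the tests are unaffected. It should be settled before the first patient is scheduled, since it fixes when the primary endpoint is measured.

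**What to change.** 1. In sections 7.1 and 9.3, change Visit 7 to Day 93 and Visit 8 to Day 94, matching the flowchart.
2. In sections 7.1 and 8, reword the sentence on the two bronchoscopies to say that the second takes place 12 weeks after dose 1. Drop the statement that both fall within 12 weeks, since they will be 92 days apart.
3. Give Visit 8 a window counted from the actual date of dose 1. The protocol offers no figure for its width, so the clinical team must set it. Record the actual days since dose 1 and dose 3 for each patient.

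The cost is four schedule lines, two sentences and one added window, with no extra visit, procedure or patient.

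If Day 84 is what the team intends, change the flowchart to Days 83 and 84 and restate the interval as about 10.6 weeks after dose 1 wherever 12 weeks now appears (14 places), including the primary endpoint. Either way, one day must govern.

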9.4 Follow up Procedures

The study participants will be referred back to the care of GSTT asthma clinic staff for continued standard care. There will be no study specific follow up.

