9.5 End of Study Definition

The study is planned over a 2 year period. Last visit of the last subject will take place by 18 months of the study start date i.e. all 12 participants would have had 2 bronchoscopies by 18 months. After this point we have planned 6 months for processing of clinical samples, molecular work, data analysis and interpretation.

10 Laboratories

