Oscillometry is a non-invasive measure of pulmonary resistance and reactance. By measuring oscillating pressures/flow signals of moving air within the lungs, when generated at different frequencies, it provides measures of airway mechanics from different lung regions. Generally lower frequencies, in particular frequency dependent changes in resistance between 5 and 20 Hz and capacitive reactance at 5 Hz are thought to reflect changes arising in the more distal airways. Oscillometry will be performed pre- and post-bronchodilator.

Fractional nitric oxide (FeNO)

FeNO is a surrogate marker of T2-airway inflammation. FeNO will be measured using a NIOX VERO device, as specified by the manufacturer's instructions. This includes collection by controlled exhalation at the recommended controlled expiratory flow rate of 50ml/s for greater than 6 seconds.

Blood sampling

Blood will be collected for routine full blood count (including blood eosinophil and basophils), biochemistry and coagulation measurements pre-bronchoscopy. In addition plasma/ serum will be stored for proteomic/nucleic acid analyses.

Bronchoscopy

Bronchoscopy will be conducted according to established guidelines, and will be performed by respiratory physicians experienced in bronchoscopy. Participants will receive nebulised salbutamol (2.5mg) and ipratropium bromide (500mcg) prior to the procedure. Local anaesthesia will be achieved with gel applied to the nasal passages and lignocaine spray to the throat, soft palate and pharynx. Intravenous sedation using midazolam (maximum 5 mg) and alfentanil (maximum 500 mcg) will be given to achieve conscious sedation. A flexible bronchoscope will then be passed either through the nose or mouth into the lungs with additional lignocaine spray being applied to prevent coughing.

- i) Bronchial brushings will be performed using single-use brushes. Up to a total of 6 brushes will be taken.

- ii) Bronchial biopsies will be performed from the lower and middle lobes using single use forceps. Up to 6 evaluable biopsies will be taken.
- iii) Bronchoalveolar lavage (BAL): the bronchoscope will be inserted in a sub-segmental bronchi and 60ml aliquots of pre-warmed 0.9% saline will be instilled followed by gentle suction to recover lining fluid. This will be repeated up to 3 times.

At the first bronchoscopy (Visit 3) samples will be collected from the right side of the lung and at second bronchoscopy (Visit 8) samples will be taken from the left side.

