An Adverse event (AE) is the development of an undesirable medical condition or the deterioration of a pre-existing medical condition following or during exposure to a pharmaceutical product, whether or not considered causally related to the product. An undesirable medical condition can be symptoms (e.g. nausea, chest pain), signs (e.g. tachycardia, enlarged liver) or the abnormal results of an investigation (e.g. laboratory findings, electrocardiogram). In clinical studies, an AE can include an undesirable medical condition occurring at any time, including run-in or washout periods, even if no study treatment has been administered. The term AE is used to include both serious and non-serious AEs.

An SAE is an AE occurring during any study phase (i.e., run-in, treatment, washout, follow- up), that fulfils one or more of the following criteria:

- Results in death
- Is immediately life-threatening
- Requires in-patient hospitalization or prolongation of existing hospitalization
- Results in persistent or significant disability/incapacity or substantial disruption of the ability to conduct normal life functions
- Is a congenital anomaly or birth defect
- Is an important medical event that may jeopardize the subject or may require medical intervention to prevent one of the outcomes listed above

An adverse drug reaction is the development of an undesirable medical condition or the deterioration of a pre-existing medical condition following or during exposure to a medicinal product, suspected to be causally related to the product.

Participants will be asked about the occurrence of any AEs at each visit and will be asked to report AEs to the study direct care team between visits. AEs will be assessed by the CI/PI for causality, intensity, seriousness and expectedness. All AEs will be recorded in the CRF and reported to the Sponsor as per their guidelines. Any adverse events that do occur and are considered by the PI to be related to the investigations will be expedited to the Sponsor and REC within 7 days. Lists of the AEs will be provided to the Sponsor when requested.

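### Scheduled adverse-event enquiry ends at Visit 8, the day of the second research bronchoscopy, so half of the planned bronchoscopies have no active safety enquiry after the procedure day

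*Protocol*

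**What the plan says.** **Last visit.** The visit lists in sections 7.1 and 9.3 end with "Visit 8: Day 84 Bronchoscopy". The flowchart in section 7.2 places the same visit on Day 94. No visit follows it in either place.

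**What is done at that visit.** Section 10.3 describes sedation, up to 6 brushings, lavage with 60 ml aliquots repeated up to 3 times, and biopsies: "Up to 6 evaluable biopsies will be taken".

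**How adverse events are found.** Section 11: "Participants will be asked about the occurrence of any AEs at each visit and will be asked to report AEs to the study direct care" (quotation cut short; the self-reports go to that team in the intervals between visits). In the flowchart, the row "Collection of adverse events (AE") has its last mark under Visit 8, with no later column.

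**After Visit 8.** Section 9.4: "The study participants will be referred back to the care of GSTT asthma clinic staff for continued standard care". The next sentence is "There will be no study specific follow up". Section 7.1 adds that patients are seen in the NHS severe asthma clinic as their condition requires. It also says that information on clinical condition is taken from the notes during the study, and that clinical-measure data are mined after participants return to NHS care.

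**What reporting depends on.** Under section 11, adverse events judged related to the investigations go to the sponsor and the ethics committee within 7 days, and all SAEs go to the sponsor within 24 hours of awareness. Under section 11.1, related and unexpected SAEs go to the ethics committee within 15 days of the chief investigator becoming aware.

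**The concern.** Benralizumab is given here as approved NHS treatment, so the two bronchoscopies are the main risk that the research itself adds. The protocol recognises this risk in section 8.2, which excludes people for whom bronchoscopy or sedation would be high-risk.

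Some complications of sedation, biopsy, brushing and lavage would show only after the participant has gone home. After the first procedure, the schedule brings the participant back for a visit at which adverse events are asked about. After the second, it does not. An exacerbation, infection or bleed that appears after the participant leaves Visit 8 is therefore not asked about, and the study may never learn of it. The 24-hour and 15-day clocks start from awareness, and the 7-day duty requires the investigator to have assessed the event, so an event that nobody hears of triggers none of them.

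**Working it through.** The protocol gives no figure of its own to reproduce. The check is a count and some date arithmetic from the visit schedule.

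**Inputs**
- Participants and procedures: section 9.5, "all 12 participants would have had 2 bronchoscopies by 18 months".
- First bronchoscopy: Visit 3, Day 2 (sections 7.1, 7.2 and 9.3).
- First later contact with adverse-event enquiry: "Visit 4: Day 10 Subject receives benralizumab dose 1 (30mg subcutaneous injection") (section 9.3).
- Second bronchoscopy: Visit 8, Day 84 (sections 7.1 and 9.3) or Day 94 (section 7.2).
- Later study contacts: none (section 9.4).

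**Number of procedures.** 12 participants × 2 bronchoscopies = 24, of which 12 are first and 12 are second procedures.

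**Interval to the next scheduled enquiry**

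| Procedure | Day | Next scheduled enquiry | Interval |
|---|---|---|---|
| First bronchoscopy | 2 | Visit 4, Day 10 | 10 − 2 = 8 days |
| Second bronchoscopy | 84 or 94 | none | no enquiry after the procedure day |

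**Share without a later enquiry.** 12 / 24 = 50%. The Day 84 versus Day 94 discrepancy needs reconciling in its own right, but it does not alter this result because nothing is scheduled after either date.

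**Does self-report fill the gap?** Section 11 asks for reports between visits. Visit 8 has no later visit, so on its wording the request does not clearly reach past that day.

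**Does the notes review fill the gap?** Last visits are due by month 18 of a 24-month study, so at least 24 − 18 = 6 months of study time follow every Visit 8, and the notes remain open to the team. But section 7.1 speaks of clinical condition and clinical measures. It does not name adverse events, link the review to the bronchoscopy or fix a time for it.

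**The case against.** The strongest reply is that participants are not lost from view. They return to the same trust's asthma service, and section 9.1 says that the asthma care team is integrated with the research team. The notes are read while the study runs, and the SAE duty in section 11 carries no cut-off. A complication brought to that clinic could well reach the investigators and start the reporting clock. This stands as far as it goes. Such capture is passive, however. It depends on the participant attending that service and on someone recognising the event as related to the procedure.

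Visit 4 is also scheduled as the first dosing visit, not as a post-bronchoscopy check, so its 8-day interval is a convenient match and not a standard set by the protocol. The trust's bronchoscopy aftercare arrangements are not visible here and may include some contact.

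Four stronger readings are tempting, and the protocol does not support them:
- *That it rules out any follow-up.* Section 9.4 excludes study-specific follow-up only, and provides for standard care in the preceding sentence.
- *That it sets an adverse-event cut-off on the day of Visit 8.* No closing date is stated. The end of scheduled enquiry follows from the visit schedule; on the collection window itself the protocol is silent.
- *That a reported safety estimate would be biased.* No safety endpoint and no comparison of the two procedures appears in sections 7.1, 10.3 or 14.2, so there is no estimate to bias.
- *That the SAE definition proves a missing phase because it mentions follow-up.* That sentence is generic. It also names run-in and washout, which this study does not have.

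A reader might also calculate that the fourth dose falls on Day 66 + 56 = Day 122, which is 38 days after Day 84 or 28 days after Day 94, and treat that as the delay before anyone would hear of an event. It is not a limit, because section 7.1 has patients seen as their condition requires.

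**Conclusion.** The point holds as a gap in active safety enquiry. As scheduled, 12 of 24 planned research bronchoscopies (50%) have no adverse-event enquiry after the procedure day, while the other 12 have one 8 days later, and no AE or SAE collection window is defined after Visit 8. The consequence lies in participant protection and ethics-committee reporting, not in any efficacy result.

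The count assumes that exactly 12 participants have both procedures. Section 8 allows dropouts to be replaced. Replacement would add first bronchoscopies and could lower the percentage, but the 12 second procedures would be unchanged. The protocol gives no complication rate, so the number of events that might be missed cannot be estimated. This is a cheap improvement that should be made, not a flaw that undermines the study.

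**What to change.** Amend section 9.4, the section 7.2 flowchart and section 11 together so that they agree on three things:
1. AE and SAE collection stays open for a stated period after Visit 8, with a stated closing point.
2. The existing team makes one telephone adverse-event enquiry after the second bronchoscopy. Matching the 8 days already present after the first is one reasonable choice.
3. Participants are asked to report events to the team until that contact has taken place.

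If the notes review in section 7.1 is meant to contribute to safety data, it should be named as a source of adverse events and given the same window.

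The cost is protocol wording, one flowchart column, 12 short calls and about one more week of participation for each person. Treatment and the existing visits are untouched.
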